6 STUDY INTERVENTION

6.2 STUDY INTERVENTIONS(S) ADMINISTRATION

6.1.1 Study Intervention Description

The study will use the dietary supplement Nicotinamide Riboside or a placebo capsule. Niagen® is a commercially-available form of nicotinamide riboside (NR). The nucleoside NR is a single chemical moiety containing nicotinamide and ribose.²² NR is a form of vitamin B3 present in trace amounts in foods like milk, yeast extract and beer. It is also postulated that NR is generated in the gastrointestinal tract as part of dietary NAD+. Thus, humans are constantly exposed to NR from the diet, albeit at low levels. Considering the clinical investigation is designed to study the relationship between a dietary supplement's effect on structure or function in humans or to characterize the mechanism by which a dietary supplement acts to maintain such structure or function, this study would not need to be conducted under an IND. Under the Dietary Supplement Health and Education Act of 1994, a dietary supplement is not considered a drug and is not subject to the premarket approval requirements for drugs if the intended use for which it is marketed is only to affect the structure or any function of the body (i.e., not intended to be used for a therapeutic

Abbreviated Title: NR in psoriasis

Version Date: 07/21/2023

purpose). Similarly, whether an IND is needed for a clinical investigation evaluating a dietary supplement is determined by the intent of the clinical investigation. If the clinical investigation is intended only to evaluate the dietary supplement's effect on the structure or function of the body, an IND is not required.

6.1.2 Dosing and Administration

N/A

6.1.3 Dose Escalation

N/A

6.1.4 Dose Limiting Toxicity

N/A

6.1.5 Dose Modifications

N/A

6.1.6 Drug Administration

Subjects will take two capsules by mouth (250mg NR capsules or placebo) twice daily for a total of 4 weeks (+/- up to 5 days if needed). Capsules must be taken whole and may be taken with or without food. Doses should be approximately 12 hours apart but there should be a minimum of 6 hours between doses. If a dose is missed and it is more than 6 hours before the next dose is due then the dose can be taken. If a dose is missed and it is less than 6 hours before the next dose is due then the missed capsules should be skipped.

6.2 PREPARATION/HANDLING/STORAGE/ACCOUNTABILITY

6.2.1 Acquisition and Accountability

Both the NR and placebo will be obtained from Chromadex. It will be stored and dispensed by the NIH CC Pharmacy. Unused product will be returned to the clinical center and destroyed.

6.2.2 Formulation, Appearance, Packaging, and Labeling

Common name: Nicotinamide Riboside Chloride

Product name: Niagen

Chemical name: 3-(Aminocarbonyl)-1-β-D-ribofuranosyl-pyridinium chloride (1:1)

Daily dose: 1000 mg x 4 wk,

Route of administration: oral

Dosing instructions: 500 mg (2 capsules) twice daily Supply:Supplements will be obtained from Chromadex.

Toxicology: None known

Drug Interactions: None known

The capsules will be put into individual bottles, labeled and dispensed by the NIH Clinical Center pharmacy. The label will include at a minimum the study ID and instructions for taking the supplement or placebo.

The placebo will be manufactured and supplied by Chromadex to match the active supplement.

Abbreviated Title: NR in psoriasis

Version Date: 07/21/2023

6.2.3 Product Storage and Stability

NR and placebo will be stored in the pharmacy at room temperature in light restricted containers.

6.2.4 Preparation

N/A

6.3 MEASURES TO MINIMIZE BIAS: RANDOMIZATION AND BLINDING

[name] (BioStatistical Co-Investigator on the study) will devise a randomization code. The code will be employed by the pharmacy to dispense the study pills. The study team will be blinded to the code until enrollment is complete and the assays performed for the primary end point.

6.4 STUDY INTERVENTION COMPLIANCE

Study capsule compliance will be assessed based on patient report and we will perform capsule count at Visit 2. If Visit 2 takes place remotely, the investigator will observe the research subject counting the remaining pills. Blood NAD⁺ metabolic intermediate levels will be tested at visit 2 to confirm compliance.

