7.2 PARTICIPANT DISCONTINUATION/WITHDRAWAL FROM THE STUDY

Participants are free to withdraw from participation in the study at any time upon request. An investigator may discontinue or withdraw a participant from the study for the following reasons:

- 1) Subject taking less than 75% of their capsules
- 2) Subject found to be pregnant or wishes to breastfeed during the study will automatically be withdrawn
- 3) If subject no longer wish to participate
- 4) Subject's non-compliance or per PI discretion for development of a condition that may independently affects immune activity.

Prior to removal from study, any subject who has started the study intervention should complete a safety visit. For subjects who complete the study, this would be included in Visit 2. If a subject requests withdrawal early for any reason, we will make every effort to have them complete an

Abbreviated Title: NR in psoriasis

Version Date: 07/21/2023

unscheduled safety visit..

The reason for participant discontinuation or withdrawal from the study will be recorded in the source document. Subjects who sign the informed consent form and are randomized but do not receive the study intervention may be replaced. Subjects who sign the informed consent form, and are randomized and receive the study intervention, and subsequently withdraw, or are withdrawn or discontinued from the study, will be replaced until the recruitment goals of 18 NR and 9 placebo subjects have completed the protocol. Participants who are withdrawn for reasons that are temporary, such as an infectious disease or administration of an immunization, may be re-screened and if they meet eligibility then re-enrolled with a new study id.

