9.2 SAMPLE SIZE DETERMINATION

Sample size calculations for this pilot study were based on the two-sample t-test assuming equal variances with a two-sided alpha of 0.05 and a 2:1 (unequal) allocation of subjects NR: placebo. A previous in-vitro study (unpublished to data) yields data for IL-17 levels (pg/ml) for T-cells extracted from psoriatic subjects at baseline and after 72 hours of exposure to 0.5 mM nicotinamide riboside (NR). The observed mean change in IL-17 cytokine release was 329 pg/ml (from 600 to 271 pg/ml) with a standard deviation of 185.74 for the 72-hour changes. For the proposed in-vivo study, we assume a similar change in mean IL-17 (and standard deviation) for psoriatic subjects treated with NR for 4 weeks. For the control subjects receiving placebo, we assume a mean baseline to 4 weeks change in IL-17 of 0 and an equal standard deviation of 185.74 for the 4-week changes.

In the table below, we present power calculations for various scenarios. With 18 subjects on NR and 9 on placebo, the study will have 98% power to detect a difference of 329 pg/ml in the mean baseline to 4-week changes between the two study groups (scenario 1). Note that there will still be 82% power to detect a smaller mean difference of 229 pg/ml between the two study arms (a 100 pg/ml difference less than that achieved in the in-vitro study) should the control subjects exhibit up to a 100 pg/ml decrease in IL-17 due to a placebo effect (scenario 2). Furthermore, even with a loss to follow-up of 3 subjects (2 in the NR arm, 1 on placebo), the study will have 97% power to detect a mean change of 329 pg/ml (scenario 3), and a reduced power just under 80% for a strong placebo effect with a mean difference = 229 pg/ml (scenario 4). Therefore, we request approval to screen up to a total of 40 subjects to account for possible treatment non- compliance and/or study dropouts (18 NR + 9 placebo completing study) and to achieve the objectives of this pilot study.

Scenario	1	2	3	4
#Subjects treated with NR	18	18	16	16
# subjects on placebo	9	9	8	8
Difference in means	329	229	329	229
Power	98%	82%	97%	77%

Abbreviated Title: NR in psoriasis

Version Date: 07/21/2023

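### Does the NAD+ test in section 6.4 leave placebo compliance unchecked, and does the plan need changing for it?

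*Combined protocol and SAP*

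**What the plan says.** Section 6.4 names three compliance measures. The first two are what the participant reports and a capsule count at visit 2, which the investigator watches if the visit is remote. The third is a blood test: NAD+ "metabolic intermediate levels will be tested at visit 2 to confirm compliance". No cut-off is given, no arm is named, and there is no rule for a result that disagrees with the capsule count. The specimen table in section 8.2.2 draws the NAD+ blood at baseline and at 4 weeks.

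Section 7.2 lets the investigator withdraw a participant on several grounds. The first is "Subject taking less than 75% of their capsules". The fourth is "non-compliance or per PI discretion for development of a condition that may independently affects immune activity", which is tied to no particular measure. Participants withdrawn after starting capsules "will be replaced until the recruitment goals of 18 NR and 9 placebo subjects have completed the protocol". The Schedule of Activities attaches a threshold of at least 75% to the pill count.

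On blinding, section 6.3 states: "The study team will be blinded to the code until enrollment is complete and the assays performed for the primary end point". Section 6.2.2 says of the comparator: "The placebo will be manufactured and supplied by Chromadex to match the active supplement". Section 9.2 asks to "screen up to a total of 40 subjects to account for possible treatment non- compliance and/or study dropouts".

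**The concern.** Section 2.2 describes NR as a precursor for NAD+ synthesis, and section 2.3.1 cites a doubling of blood NAD+ in eight healthy volunteers on escalating NR. A matched placebo with no described tracer should leave the level unchanged whether or not it is taken. The purpose stated in section 6.4 therefore cannot be met for one arm.

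Three consequences would matter if they occurred:

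- An NAD+ level that has not risen might be counted as non-compliance under the fourth ground of 7.2. Withdrawal and replacement would then depend on arm, and so would the make-up of the 18 + 9 completers.
- The study team could not correct for arm while replacement is under way, because section 6.3 keeps it blinded until enrolment and the primary assays are finished.
- Anyone who saw NAD+ results early would have a clue to allocation.

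**Working it through.** **The plan's own figures.** The plan gives no figure for how many participants NAD+ can confirm. Its numerical statement about the 18 + 9 design is the power table in 9.2. I recomputed it with the noncentral t distribution: df = n1 + n2 − 2, noncentrality = difference / [185.74 × √(1/n1 + 1/n2)], two-sided alpha 0.05.

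| Scenario | NR + placebo | Difference (pg/ml) | Noncentrality | Power, plan | Power, recomputed |
|---|---|---|---|---|---|
| 1 | 18 + 9 | 329 | 4.34 | 98% | 98.6% |
| 2 | 18 + 9 | 229 | 3.02 | 82% | 82.7% |
| 3 | 16 + 8 | 329 | 4.09 | 97% | 97.4% |
| 4 | 16 + 8 | 229 | 2.85 | 77% | 77.7% |

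The table reproduces to within one percentage point. NAD+ does not enter it.

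**What NAD+ can confirm.** Assume a perfect assay, full compliance and a placebo that does not raise NAD+.

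- With 18 + 9 completers: 18/27 = 66.7% confirmed and 9/27 = 33.3% not confirmable.
- With 16 + 8: 16/24 = 66.7%.

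The share is two thirds whatever the size, because it is the allocation ratio.

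**What the capsule count covers.** Section 6.1.6 has every participant take 2 capsules twice daily, so 4 a day in either arm, for 28 days give or take 5.

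| Days | Capsules due | 75% |
|---|---|---|
| 23 | 4 × 23 = 92 | 69 |
| 28 | 4 × 28 = 112 | 84 |
| 33 | 4 × 33 = 132 | 99 |

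The threshold can be computed without knowing the arm, for 27 of 27.

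**Side by side.** Section 6.4 (capsule count), the Schedule of Activities (75% on the pill count) and the first ground of 7.2 (75% of capsules) use the same measure, and they agree. No section gives NAD+ a threshold or an action. Analysis populations in 9.3 are marked not applicable, and 9.4.2 does not mention NAD+.

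**Could NAD+ be decisive under 7.2?** Suppose that a level that has not risen counted as non-compliance and always led to withdrawal. No placebo participant could then complete (0 of 9), so the replacement goal in 7.2 could never be reached. An arm-specific version would need the code, which 6.3 withholds during replacement. Neither version can be run under the plan. The workable reading is that the capsule count serves 7.2 in both arms and NAD+ is interpreted after unblinding.

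**The case for a change.** The strongest case for a change is that the fourth ground of 7.2 is separate from the capsule ground and undefined. Because 6.4 calls NAD+ a compliance test, an investigator could bring a low result under it at discretion, participant by participant, without a blanket rule. The plan does not say which measure prevails when they disagree, or when the team sees NAD+ results. The table in 8.2.2 puts the NAD+ and PBMC blood on one line with one destination, so early sight of results is conceivable. A few sentences would settle this at almost no cost.

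The silence is real, and so is the inability to verify placebo intake biochemically. The step from there to harm is not supported. The fourth ground could equally refer to missed visits, diet or barred supplements. Nothing sends NAD+ results to the team early, and batched testing after the primary assays fits both 6.3 and 6.4. Nothing shows that the same staff run both assays.

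Misclassification rates could be calculated, but only by inventing rates of non-compliance and assay error that the documents do not give. Borrowing the loss of three participants from 9.2 does not help: that is loss to follow-up, and people lost before visit 2 provide no visit 2 sample.

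The test also has some use on placebo. A raised level there could point to NR or to vitamin B products barred by 6.5.

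**Conclusion.** No change is needed. The limitation is that NAD+ can corroborate intake in at most 18 of 27 completers, all on NR. It concerns a supportive test and restates the 2:1 allocation. Compliance in both arms is assessed by report and capsule count, on a threshold that the plan states consistently. No effect on the IL-17 endpoint, the stated power, the sample size or any withdrawal is shown. What is missing is a note on how to read the NAD+ result, and analysts would fill that sensibly by reporting it by arm after unblinding as a measure of NR exposure.

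This rests on three assumptions: the placebo does not raise NAD+, NAD+ results are not used on their own to withdraw participants, and they do not reach the blinded team before the point set in 6.3. The documents contain nothing against any of these, though they state none of them outright. Evidence that NAD+ had driven withdrawals, or had been seen early, would reopen the question.

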6.5 CONCOMITANT THERAPY

Subjects should not take any biologic immune modifying agents, other multivitamins, vitamin B or tryptophan supplements for the duration of the study.

7 STUDY INTERVENTION DISCONTINUATION AND PARTICIPANT DISCONTINUATION/WITHDRAWAL

7.1 Discontinuation Of Study Intervention

The supplement has a good safety record and we do not expect any significant adverse events. However, if a grade 3 or higher adverse event related to the supplement occurs, the study will be halted pending discussions with the NIH IRB and the NHLBI Clinical Director.

7.2 PARTICIPANT DISCONTINUATION/WITHDRAWAL FROM THE STUDY

Participants are free to withdraw from participation in the study at any time upon request. An investigator may discontinue or withdraw a participant from the study for the following reasons:

- 1) Subject taking less than 75% of their capsules
- 2) Subject found to be pregnant or wishes to breastfeed during the study will automatically be withdrawn
- 3) If subject no longer wish to participate
- 4) Subject's non-compliance or per PI discretion for development of a condition that may independently affects immune activity.

Prior to removal from study, any subject who has started the study intervention should complete a safety visit. For subjects who complete the study, this would be included in Visit 2. If a subject requests withdrawal early for any reason, we will make every effort to have them complete an

Abbreviated Title: NR in psoriasis

Version Date: 07/21/2023

unscheduled safety visit..

The reason for participant discontinuation or withdrawal from the study will be recorded in the source document. Subjects who sign the informed consent form and are randomized but do not receive the study intervention may be replaced. Subjects who sign the informed consent form, and are randomized and receive the study intervention, and subsequently withdraw, or are withdrawn or discontinued from the study, will be replaced until the recruitment goals of 18 NR and 9 placebo subjects have completed the protocol. Participants who are withdrawn for reasons that are temporary, such as an infectious disease or administration of an immunization, may be re-screened and if they meet eligibility then re-enrolled with a new study id.

7.3 LOST TO FOLLOW-UP

A participant will be considered lost to follow-up if he or she fails to return for the scheduled visits and is unable to be contacted by the study site staff.

The following actions must be taken if a participant fails to return to the clinic for a required study visit:

- The site will attempt to contact the participant and reschedule the missed visit, specify time frame and counsel the participant on the importance of maintaining the assigned visit schedule and ascertain if the participant wishes to and/or should continue in the study.
- Before a participant is deemed lost to follow-up, the investigator or designee will make every effort to regain contact with the participant (where possible, 3 attempts at contact) These contact attempts should be documented in the participant's medical record or study file.
- Should the participant continue to be unreachable, he or she will be considered to have withdrawn from the study with a primary reason of lost to follow-up.

8 STUDY ASSESSMENTS AND PROCEDURES

8.1 SCREENING PROCEDURES

Subjects with mild to moderate psoriasis will be recruited from [name] psoriasis clinic at the NIH or from outside and self- referrals If a subject is recruited from a source outside the NIH then the screening and/or baseline visit #1 will be in person. The remainder of the visits may be via telehealth.

Screening activities performed prior to obtaining informed consent

Minimal risk activities that may be performed before the subject has signed a consent include the following:

- Email, written, in person or telephone communications with prospective subjects
- Review of existing medical records to include H&P, laboratory studies, etc.

Once the research team has identified a potential subject for the study, the subject will be asked to come to the NIH or complete a Telehealth Screening Visit. The study team will consent the subject, allowing time for the subjects to ask questions and make a voluntary decision.

Abbreviated Title: NR in psoriasis

Version Date: 07/21/2023

Once the subject signs the consent, the following tests will be done at the Screening Visit unless any of the tests have been performed under another NIH protocol 2 weeks prior to signing the consent (unless otherwise stated).

Screening Visit (May be combined with Visit 1):

- Basic Metabolic Panel
- Hepatic Panel + uric acid
- CBC + Differential
- Serum pregnancy test for women with childbearing potential (within the past 24 hours)
- History +/- physical exam (physical exam will not be performed at TeleHealth visit)

8.2 EFFICACY ASSESSMENTS

This study is designed to study the relationship between a dietary supplement's effect on structure or function in humans or to characterize the mechanism by which a dietary supplement acts to maintain such structure or function. It is not designed as an efficacy study. Therefore, visits will focus on safety assessments as well as the collection of research blood and skin biopsies (optional). These collections will be performed at the NIH CC phlebotomy department when feasible however collection at an outside laboratory, such as a commercial or hospital-based lab, may be arranged if needed.

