1.3 SCHEDULE OF ACTIVITIES (SOA)

EVALUATION AND ASSESSMENTS	Screening (A)	Baseline Visit*	28 day Visit *	Safety visit (if applicable)
PROTOCOL TIMEPOINT VISITS		1	2	3
		D0	D28	
Window +/- days	-120Days		+/- 7 D	
Assessments & Consents				
Review Inclusion/Exclusion Criteria	X			
Medical History	X			
Physical Examination	X ³	X ³	X ³	X ³
Medication Review	X	X	X	
Vital Signs		X ³	X ³	X ³
Consent to Study	X	X		
Adverse Event Review			X	X
CHEMISTRY LABS				
Female, Pregnancy Test (blood or urine)	X ¹	X ¹	X ¹	
Acute Care Panel	X	X	X	X
Mineral Panel		X	X	X
Hepatic Panel	X	X	X	X
hs-CRP		X	X	X
Uric Acid	X			
Fasting Lipid Panel		X	X	
HEMATOLOGY LABS				
CBC with differential	X	X	X	X
Research Samples				
PBMC's		X	X	
Serum		X	X	
Procedures				
Skin Punch Biopsy (lesion and non-lesion)		X ³	X ³	
PASI (Psoriasis Area and Severity Index)	X			
Study Medication				
Dispense study pills		X		
Compliance (pill count)			X ²	
Return of study pills			X	
A. Labs and assessments may be used for baseline visit if performed within 14 days				
B. Unscheduled safety visit for those patients with clinically significant ongoing adverse events from month 1 visit or reported to site within 7 days from last dose of study drug. All procedures or testing noted above are optional.				
X ¹ = Pregnancy testing for women with childbearing potential				
X ³ = Optional				
X ² = compliance to be greater than or equal to 75%				
*Study visits are defined by the period of time necessary to complete events described in the protocol and may span several days.				

Abbreviated Title: *NR in psoriasis*

Version Date: *07/21/2023*

All study visits may be performed in person at the NIH CC or virtually using NIH approved TeleMedicine software and approved NIH TeleMedicine guidance. In the event the subject is not able to come to the NIH CC the consent may be obtained by phone, vital signs are optional and reported based on subject's own measurements (if possible), physical exam is optional and none of these changes will be considered a protocol deviation. If there are remaining tablets, they will be returned to the research team at first possible opportunity following NIH pharmacy direction.

Abbreviated Title: NR in psoriasis

Version Date: 07/21/2023

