9 STATISTICAL CONSIDERATIONS

9.1 STATISTICAL HYPOTHESIS

Supplementation with NR will blunt systemic immune activation in mild/moderate psoriasis.

Primary Endpoint(s): The primary outcome will be the change in the T_H17 cell cytokine IL-17 secretion in response to T-cell differentiation comparing the baseline to NR response after 28 days.

Exploratory Endpoint(s):

- Evaluate the effect of NR on the T cell transcriptome
- Explore the effect of NR on low-density granulocytes and neutrophils

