9.4 STATISTICAL ANALYSES

9.4.1 General Approach

9.4.2 Analysis of the Primary Endpoints

The primary outcome will be the change in the T_H17 cell cytokine IL-17 secretion in response to T-cell differentiation comparing baseline levels versus their respective response to NR or placebo. The comparisons will be performed using paired two-tailed Student t-tests or if the data is not normally distributed, by the Wilcoxon test. Significance will be tested at the 0.05 alpha level in this pilot study.

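### Research blood may be drawn at the NIH at baseline and at an outside laboratory at day 28, and the paired within-arm test cannot tell a handling shift from an NR effect

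*Combined protocol and SAP*

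**What the plan says.** **Where blood is drawn.** Section 8.2 has research samples taken at the NIH Clinical Center when feasible, and then allows that "collection at an outside laboratory, such as a commercial or hospital-based lab, may be arranged if needed".

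**Which visits are in person.** For people recruited outside the NIH, Section 8.1 says "the screening and/or baseline visit #1 will be in person" and then "The remainder of the visits may be via telehealth". The notes to the schedule in Section 1.3 are broader: "All study visits may be performed in person at the NIH CC or virtually using NIH approved TeleMedicine software". The only scheduled visit after baseline is day 28.

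**What is controlled.** The table in Section 8.2.2 gives blood volumes, tube types, a 48-hour collection window either side and the receiving laboratory. It sets no same-route rule, transport condition or limit from collection to cell isolation. Section 10.6 covers specimens only in general monitoring terms.

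**Endpoint and test.** Section 9.1 defines the primary outcome as a change in IL-17 secretion, "comparing the baseline to NR response after 28 days". Section 9.4.2 describes the analysis as "comparing baseline levels versus their respective response to NR or placebo" and continues: "The comparisons will be performed using paired two-tailed Student t-tests or if the data is not normally distributed, by the Wilcoxon test". It names no between-arm test. Section 9.2, however, says: "Sample size calculations for this pilot study were based on the two-sample t-test assuming equal variances".

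**The concern.** The preliminary-data method in Section 2.2 isolates CD4+ T cells from fresh PBMCs and cultures them for three days before IL-17 is measured. The trial's assay is presumably the same, though Section 8 does not say so. In a functional assay on living cells, transport and delay before isolation are plausible sources of variation. Using one receiving laboratory standardises the assay but not what happens to the blood before it arrives.

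The visit rules make one mismatch easier than its reverse. A participant who attends baseline in person and is then followed remotely can have an outside draw only at day 28. If outside handling moves IL-17, the movement enters the change from baseline. A within-arm paired test attributes that whole change to the intervention. A downward shift would look like the hypothesised effect, and an upward shift would hide a real one. Blinding does not help, because a handling shift does not depend on anyone knowing the code. Without a record of site and time to isolation, the problem could not be examined afterwards.

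**Working it through.** **Inputs from Section 9.2:** SD of change 185.74 pg/ml; baseline mean 600 pg/ml; 18 NR and 9 placebo completers; two-sided alpha 0.05; planned differences 329 and 229 pg/ml.

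**Assumptions (not in the documents):** share f of day-28 draws taken off-site while baseline was at the NIH; reading c lower per off-site draw, so shift s = c × 600; true NR effect zero for the false-positive figures.

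**1. The plan's own power.** For the two-sample t-test, noncentrality = difference / [SD × √(1/n1 + 1/n2)], with n1 + n2 − 2 degrees of freedom. The four scenarios give 98.6%, 82.7%, 97.4% and 77.7%, against the stated 98%, 82%, 97% and 77%. The plan's figures reproduce.

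**2. False positives of the paired test, n=18.**
- Mean shift = f × s.
- SD of change = √[185.74² + f(1 − f)s²].
- Noncentrality = mean shift / (SD/√18), with 17 degrees of freedom and critical t of 2.110.
- With no added variance, significance needs a mean change of 2.110 × 185.74/√18 ≈ 92 pg/ml.

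Example, f = 1/3 and c = 20%: s = 120; mean shift = 40; SD = √(34,499 + 0.2222 × 14,400) = 194.2; noncentrality = 40/(194.2/4.243) = 0.874; rejection rate 13.1%.

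| Off-site share at day 28 | 10% low (60 pg/ml) | 20% low (120 pg/ml) | 30% low (180 pg/ml) |
|---|---|---|---|
| one sixth | 5.5% | 7.0% | 9.3% |
| one third | 7% | 13% | 22% |
| one half | 10% | 23% | 42% |

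The nominal rate is 5%. Because the test is two-sided, the same rates apply to readings that are high by the same amount.

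**3. The placebo arm as an informal check.** In simulation (100,000 runs per setting, no NR effect, same off-site probability in both arms), half off-site with a 100 pg/ml shift gives a significant NR arm in 18% of trials. NR is significant while placebo is not in 16%. With nine placebo subjects, reading the two paired tests side by side gives little protection.

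**4. Between-arm test of changes.** The simulation covered off-site shares of 25% to 100% and shifts of 50 to 200 pg/ml. The two-sample test rejected in 4.9% to 5.1% of trials in every setting, because a shift common to both arms cancels in expectation. The remaining cost is variance. With one third off-site:

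| Reading | SD of change | Power at 229 pg/ml | Power at 329 pg/ml |
|---|---|---|---|
| no shift | 185.7 | 82.7% | 98.6% |
| 20% low | 194.2 | 79% | 98% |
| 30% low | 204.2 | 75% | 97% |

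For example, at 30% low and 229 pg/ml the noncentrality is 229/(204.2 × 0.408) = 2.75, against 3.02 with no shift.

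**The case against.** **The bias comes from the choice of test.** A handling shift is one of several things, along with assay drift and regression to the mean, that a within-arm test cannot separate from treatment. Allocation is randomised and blinded, so off-site draws should be about equally likely in both arms and a between-arm test deals with the systematic part. This stands, and it is why the fix includes the test as well as the blood draw.

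**Discordant pairs may be rare.** A reader might infer that the visit rules pair NIH baseline draws with outside day-28 draws as a matter of course. The documents do not support that:
- NIH collection is the default, and outside collection is a contingency.
- The synopsis limits screening to people living locally.
- The in-person rule covers only people recruited outside the NIH, and it governs visits, not blood draws.
- Baseline may itself be remote, so both draws could be off-site.

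The pattern is permitted, not prescribed, so the one-sixth row is a better guide than the one-half row.

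**Size and direction have no source.** Nothing in the documents says that delay lowers IL-17. Preliminary results were normalised to cell number, which, if carried into the trial, would offset simple cell loss but not altered cell function. This stands, and the figures are only a range under assumptions.

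**A strict same-site rule could lose primary samples.** Someone unable to return at day 28 would have no compliant draw, and Section 7.2 would then have them replaced if withdrawn. This also stands, and the fix is worded to avoid it.

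**Conclusion.** The gap is real and its likely effect is modest. The plan permits discordant collection for a live-cell primary endpoint, sets no limit on time to isolation, and names an analysis that cannot separate handling from treatment. If one sixth of day-28 draws were off-site, the false-positive rate would rise from 5% to between 5.5% and 9.3% for readings 10% to 30% low. Rates of 22% or 42% need off-site shares of one third or one half together with a 30% shift, and the documents give no reason to expect that.

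A reader might also conclude that outside collection would bias the trial under any analysis. It would not. In a between-arm test of changes the systematic part cancels on average, provided that off-site draws are equally likely in both arms. What remains is chance imbalance with nine placebo subjects and a loss of power, from 82.7% to about 75–79% at 229 pg/ml with one third off-site and readings 20–30% low. If no outside draws occur, there is no harm. This is an inexpensive improvement and does not invalidate the design.

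**What to change.** 1. In Section 8.2, state that each participant's baseline and day-28 research draws use the same collection route and the same collection-to-isolation limit wherever possible. If that is not possible, keep the sample and flag it.
2. Record collection site and time from collection to isolation for both draws.
3. In Section 9.4.2, base the conclusion about NR on the between-arm comparison of changes, in line with Section 9.2. Paired within-arm results can be reported as descriptive.
4. Prespecify a sensitivity analysis that excludes participants whose two draws used different routes.

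The cost is a short addition to Section 8.2, two CRF fields, one extra analysis, and less freedom to use a local draw at day 28 only. Local collection at both visits stays available, and no primary sample is discarded. The between-arm test needs no more subjects, because the trial is already sized for it.
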